## 7.7.4. Toxicity Management of Immune-Related Adverse Events Observed With Nivolumab

Adverse events related to the use of immunomodulatory therapies such as nivolumab are immunologic in etiology. They may occur at any time from shortly after first dose **to many months after the last dose** and can affect multiple organs simultaneously. Most irAEs observed with anti-PD-1/programmed cell death ligand 1 (PD-L1) mAbs are reversible with early detection and treatment discontinuation or treatment with immunomodulating agents such as corticosteroids. Investigators should exercise clinical judgment regarding best clinical management, based on the symptoms and condition of the individual participant.

#### General instructions:

- Monitor all participants closely for signs and symptoms of irAEs, including signs related to gastrointestinal, endocrine, hepatic, ophthalmologic, or cardiac irAEs.
- Early evaluations with radiographic imaging, relevant laboratory testing, procedures and speciality consultation should be considered.
- Initiate high dose steroid (prednisone 1-2 mg/kg) when indicated for appropriate Grade 3-4 irAEs.
- The investigator must notify the Gilead medical monitor in a timely manner upon identification of any potential irAE regardless of grade or seriousness.

• Report all irAEs that meet serious criteria in accordance with Sections 7.3.3 and 7.4.

According to the approved product label for nivolumab, patients should be monitored continuously (at least up to 5 months after the last dose) as an ADR with nivolumab may occur at any time during or after discontinuation of therapy.

For more detailed management guidance, refer to the current approved product label for nivolumab {OPDIVO 2022}.

## 7.7.5. ALT Elevation or Flare Management on Treatment and Treatment-Free Follow-up

## **On-Treatment ALT Management**

Participants with on-treatment serum ALT elevation  $> 2 \times$  nadir or  $> 2 \times$  baseline value and  $\ge 5 \times$  ULN, with or without associated symptoms should be managed according to the guidance below.

All elevated serum ALT should be confirmed as soon as possible and ideally within 3 days of receipt of results. During the visit, a clinical assessment of the participant should be performed. The assessment should include a physical examination, evaluation of the participant's mental status, and the following laboratory tests:

- Laboratory parameters: serum ALT and AST, total bilirubin, GGT, INR, and serum albumin, alcohol screening
- If the ALT elevation is confirmed, the central clinical laboratory will conduct reflex testing for plasma HBV DNA, serology for HBV (HBsAg, HBsAb, HBeAg and HBeAb), HDV, hepatitis A virus (HAV) IgM, HCV, and HEV
- Liver biopsy may be collected for participants meeting Hy's law (ALT >  $3 \times ULN$  and Total Bilirubin >  $2 \times ULN$ ; AST >  $3 \times ULN$  and Total Bilirubin >  $2 \times ULN$ ) with suspected DILI

Additional confirmatory tests such as HDV RNA, HDV IgM, and HEV RNA may be performed locally as per local regulations after further discussion with the Gilead's Medical Monitor.

Based on the results of the confirmatory tests, the following study treatment modifications are recommended (Table 6).

Table 6. Dose Modification and Monitoring

Liver Toxicity Parameters	Action
Confirmed, ALT $\geq 10 \times ULN$ without evidence of hepatic toxicity as defined below	Cohort 1: Hold VIR-2218 and SLGN treatment. Participant should be monitored weekly or more frequently if clinically indicated until ALT < 5 × ULN. Restarting VIR-2218 and/or SLGN treatment may be considered when ALT < 5 × ULN in discussion with the medical monitor. Study treatment should be restarted in line with the original assigned administration schedule.  Cohort 2: Initiate TAF 25 mg once daily and hold VIR-2218 and SLGN dose. Participant should be monitored weekly or more frequently if clinically indicated until ALT < 5 × ULN. Restarting VIR-2218 and/or SLGN treatment may be considered when ALT < 5 × ULN in discussion with the medical monitor. Study treatment should be restarted in line with the original assigned administration schedule.
Persistent ALT > 2 × baseline and $\geq$ 5 × ULN without evidence of hepatic toxicity, as defined below	Continue study treatment(s), ALT should be evaluated every 2 weeks or more frequently as clinically needed, until ALT < 5 × ULN
Confirmed ALT > 2 × nadir, with evidence of hepatic toxicity, defined as any one of the following confirmed laboratory abnormalities:  Total bilirubin > 2 × ULN  Elevated INR > 0.5 above baseline AND > ULN  Abnormal serum albumin > 1 g/dL decrease from baseline	Cohort 1: Permanently discontinue study treatment(s) except TAF 25 mg once daily. Participant should be monitored weekly until ALT < 5 × ULN, and total bilirubin, INR, and albumin values return to normal or baseline levels.  Cohort 2: Initiate commercially approved NUC treatment once daily and permanently discontinue study treatment(s). Participant should be monitored weekly until ALT < 5 × ULN, and total bilirubin, albumin, and/or INR values return to normal or baseline levels

ALT = alanine aminotransferase; INR = international normalized ratio; NUC = nucleos(t)ide(s); SLGN = selgantolimod; TAF = tenofovir alafenamide; ULN = upper limit of normal

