Persistent ALT > 2 × baseline and ≥ 5 × ULN without evidence of hepatic toxicity, as defined below	Continue study treatment(s), ALT should be evaluated every 2 weeks or more frequently as clinically needed, until ALT < 5 × ULN

Confirmed ALT $> 2 \times$ nadir, with
evidence of hepatic toxicity,
defined as any one of the
following confirmed laboratory
abnormalities:

- Total bilirubin  $> 2 \times ULN$
- Elevated INR > 0.5 above baseline AND > ULN
- Abnormal serum albumin
   1 g/dL decrease from baseline

**Cohort 1:** Permanently discontinue study treatment(s) except TAF 25 mg once daily. Participant should be monitored weekly until ALT < 5 × ULN, and total bilirubin, INR, and albumin values return to normal or baseline levels

**Cohort 2:** Initiate commercially approved NUC treatment once daily and permanently discontinue study treatment(s). Participant should be monitored weekly until ALT  $< 5 \times ULN$ , and total bilirubin, albumin, and/or INR values return to normal or baseline levels

ALT = alanine aminotransferase; INR = international normalized ratio; NUC = nucleos(t)ide(s); SLGN = selgantolimod; TAF = tenofovir alafenamide; ULN = upper limit of normal

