### 4.3. Exclusion Criteria

Participants who meet *any* of the following exclusion criteria are not eligible to be enrolled in this study:

- 1) Extensive bridging fibrosis or cirrhosis as defined clinically by any 1 of the following:
  - a) Metavir  $\geq 3$  or Ishak fibrosis score  $\geq 4$  by a liver biopsy within 1 year of screening, or, in the absence of an appropriate liver biopsy, either:
  - b) Screening FibroTest score of > 0.48 and AST to platelet ratio index (APRI) > 1 by central laboratory, or
  - c) Historical (within  $\leq 6$  months of screening) or current FibroScan with a result > 9 kPa

If liver biopsy is available, the liver biopsy result supersedes (b) and/or (c, if available)

If an appropriate liver biopsy is not available, fibrosis will be evaluated by (b) and/or (c, if available). In the event of discordance between (b) and (c), the FibroScan results will take precedence.

- 2) Participants meeting any of the following laboratory parameters at screening:
  - a) Hemoglobin  $\leq 12 \text{ g/dL}$  (for males) or  $\leq 11 \text{ g/dL}$  (for females)
  - b) White blood cell (WBC) count < 2500 cells/mm^3
  - c) Neutrophil count < 1500 cell/mm³ (or < 1000 cell/mm³ if considered a physiological variant in a participant of African descent)
  - d) ALT  $\geq$  2 × ULN (Cohort 1 only), ALT  $\geq$  5 × ULN (Cohort 2)
  - e) International normalized ratio (INR) > ULN unless the participant is stable on an anticoagulant regimen affecting INR
  - f) Albumin < 3.5 g/dL

- g) Direct bilirubin  $> 1.5 \times ULN$
- h) Platelet Count  $< 100,000/\mu$ L
- i) Positive autoantibodies, defined as any one or more of the following:
  - i) Antinuclear antibodies (ANA) > 1:80
  - ii) Smooth muscle antibodies (anti-SMA) > 1:80
  - iii) Antimitochondrial antibodies (AMA) > 1:40
  - iv) Anti-thyroid peroxidase (anti-TPO) > 35 IU/mL
- j) Estimated creatinine clearance (CLcr) < 60 mL/min (using the Cockcroft-Gault method) based on serum creatinine and actual body weight as measured at the screening evaluation, ie,

- 3) Participants in Cohort 2: Received OAV treatment for HBV within 6 months of screening. Participants who meet criteria for initiation of NUC treatment as judged by the principal investigator (PI) during screening should be excluded from Cohort 2.

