- 4) Coinfection with HIV, HCV, or HDV. Participants who are HCV antibody (Ab) or HDV Ab positive, but have a documented negative HCV RNA or HDV RNA, respectively, are eligible.
- 5) Current or prior history of HCC (eg, as evidenced by prior imaging) or screening  $\alpha$ -fetoprotein  $\geq$  50 ng/mL without imaging to rule out HCC
- 6) Current or prior history of clinical hepatic decompensation (eg, ascites, encephalopathy, or variceal hemorrhage).
- 7) Malignancy within 5 years prior to screening, with the exception of specific cancers that are cured by surgical resection (eg, basal cell skin cancer). Participants under evaluation for possible malignancy are not eligible
- 8) Significant cardiovascular, ophthalmological, pulmonary, or neurological disease in the opinion of the investigator

- 9) Diagnosis of any autoimmune disease (eg, systemic lupus erythematosus, rheumatoid arthritis, inflammatory bowel disease, ulcerative colitis, pneumonitis, autoimmune hepatitis, sarcoidosis, psoriasis of greater than mild severity, autoimmune uveitis, autoimmune nephritis, thyroiditis), poorly controlled diabetes mellitus, significant psychiatric illness, severe chronic obstructive pulmonary disease (COPD), hemoglobinopathy, retinal disease, or are immunosuppressed
- 10) Chronic liver disease of a non-HBV etiology (eg, Wilson's disease, hemochromatosis, alpha-1-antitrypsin deficiency, cholangitis), except for nonalcoholic fatty liver disease
- 11) Received solid organ or bone marrow transplant
- 12) Received prolonged therapy with immunomodulators (eg, corticosteroids) or biologics (eg, mAb, IFN, nivolumab) within 6 months of screening
- 13) Have received inactivated vaccinations (eg, injectable influenza or pneumococcal) within 4 weeks prior to randomization or received live vaccinations within 4 weeks prior to screening
- 14) Use of another investigational agent within 90 days of screening, unless allowed by the sponsor
- 15) Current alcohol or substance abuse judged by the investigator to potentially interfere with participant compliance
- 16) Known hypersensitivity to study drug or formulation excipients
- 17) Women who are breastfeeding, pregnant, or who wish to become pregnant during the course of the study
- 18) Female participants unwilling to refrain from egg donation and in vitro fertilization during and until at least 5 months after last study drug dose.

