- 19) Male participants unwilling to refrain from sperm donation during and until at least 5 months after the last study drug dose
- 20) Use of any prohibited concomitant medications as described in Section 5.4
- 21) Believed by the study investigator to be inappropriate for study participation for any reason not otherwise listed.

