### 6.1.5. Clinical Laboratory Tests/Assessments for Safety Evaluations

Blood and urine samples for safety evaluations will be collected throughout the study as outlined in Appendix 11.3.

- Hematology: hematocrit, hemoglobin, platelet count, red blood cell (RBC) count, WBC count with differential (absolute and percentage), including lymphocytes, monocytes, neutrophils, eosinophils, basophils, and mean corpuscular volume (MCV)
- Chemistry: alkaline phosphatase, AST, ALT, total bilirubin, direct and indirect bilirubin, total cholesterol, high-density lipoprotein (HDL), low-density lipoprotein (LDL), triglycerides, total protein, albumin, lactic acid dehydrogenase (LDH), creatine kinase (CK), bicarbonate, blood urea nitrogen, calcium, chloride, creatinine (see below), glucose, phosphorus, magnesium, potassium, sodium, uric acid, and lipase (reflex amylase testing is performed in participants with total lipase > 1.5 × ULN)
- Coagulation panel: prothrombin time, activated partial thromboplastin time, and INR
- Qualitative HBV serology (HBeAg and hepatitis B e antibody [HBeAb]; and HBsAg [reflex HBsAb if HBsAg is negative])
- Quantitative HBV serology (HBsAg, HBcrAg, HBeAg [if applicable], and HBV RNA)
- Serum sample for HBV viral sequencing, genotyping sample, and ddPCR
- Quantitative plasma HBV DNA
- Thyroid-stimulating hormone (TSH) levels
- Pregnancy test: serum or urine β human chorionic gonadotropin (β-hCG) pregnancy test (if positive, requires immediate confirmation with serum β-hCG)
  - Follicle-stimulating hormone (FSH) testing (FSH test is required for female participants who are < 54 years old who are not on hormonal contraception and who have stopped menstruating for ≥ 12 months but do not have documentation of ovarian hormonal failure)
- Urinalysis: appearance, blood, color, glucose, leukocyte esterase, pH, protein, urobilinogen. Reflex to microscopic urinalysis if dipstick result is abnormal.
- Urine drug (amphetamines, cocaine, methadone, opiates) and alcohol screen
- Autoantibodies: ANA, anti-SMA, AMA, and anti-TPO

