Confirmed ALT > ULN with evidence of hepatic toxicity, defined as any one of the following confirmed laboratory abnormalities:  • Total bilirubin > 2 × nadir AND > 2.5 mg/dL in the absence of Gilbert's disease  • Elevated INR > 0.5 above nadir AND > ULN  • Abnormal serum albumin > 1 g/dL decrease from baseline	Initiate NUC treatment and monitor weekly or more frequently if clinically indicated until return to baseline levels or within normal reference range. Liver biopsy may be considered if appropriate for participant management.
Confirmed, HBV DNA > 20,000 IU/mL (HBeAg positive) or > 2,000 IU/mL (HBeAg negative) and persistent ALT > ULN without evidence of hepatic toxicity, as defined above, for > 8 weeks	Initiating NUC treatment may be considered in discussion with the medical monitor.

ALT = alanine aminotransferase; DNA = deoxyribonucleic acid; HBeAg = hepatitis B e antigen; HBV = hepatitis B virus; NUC = nucleos(t)ide(s); ULN = upper limit of normal

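### The on-treatment bilirubin limit in Tables 1 and 6 can already be exceeded at entry, which leaves ALT alone to decide permanent discontinuation for those participants

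*Supplement*

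**What the plan says.** **Entry (Section 4.3).** The only bilirubin limit is exclusion 2(g), which opens "Direct bilirubin" and excludes values above 1.5 × ULN. Total bilirubin has no limit. The liver-disease exclusion reads "Chronic liver disease of a non-HBV etiology (eg, Wilson's disease, hemochromatosis, alpha-1-antitrypsin deficiency, cholangitis), except for nonalcoholic fatty liver disease" and does not name Gilbert's. What remains is the discretionary exclusion: "Believed by the study investigator to be inappropriate for study participation for any reason not otherwise listed". Section 6.1.5 shows that the routine chemistry panel includes "total bilirubin, direct and indirect bilirubin".

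**On treatment (Section 7.7.5, Table 6; synopsis Table 1).** The stopping row applies to "Confirmed ALT > 2 × nadir, with evidence of hepatic toxicity, defined as any one of the following confirmed laboratory abnormalities". Three abnormalities follow:
- total bilirubin above 2 × ULN;
- INR more than 0.5 over baseline and above ULN;
- albumin down by more than 1 g/dL from baseline.

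The action for Cohort 1 is "Permanently discontinue study treatment(s) except TAF 25 mg once daily". Cohort 2 stops study treatment permanently and starts a commercial NUC. Monitoring then runs until ALT is below 5 × ULN and the three other tests are normal or back at baseline.

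**Follow-up (Section 7.7.5, Table 7; synopsis Table 2).** The bilirubin item of the hepatic-toxicity definition is "Total bilirubin > 2 × nadir AND > 2.5 mg/dL in the absence of Gilbert's disease".

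**Lead-in to Section 7.7.5.** The on-treatment guidance covers ALT above twice nadir, or above twice baseline and at least 5 × ULN. It does not say whether the last condition belongs to both limbs.

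**The concern.** The stopping row is built as a two-part rule: an ALT rise together with a sign that liver function is affected. For a participant who entered with total bilirubin above 2 × ULN, the second part carries no information, because the entry value already satisfies it. The same unchanged value would not count under Table 7.

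The outcome is permanent loss of study treatment and, in Cohort 2, NUC treatment. That changes exposure before the FU Week 24 endpoint. NUC use also bears on the HBV DNA half of functional cure and on the secondary endpoint of remaining off NUC. Safety is a primary objective. Section 7.6 requires a laboratory abnormality that leads to discontinuation to be recorded as an AE, and Section 8.6.2 counts any AE leading to premature discontinuation as treatment-emergent. Such a stop therefore reaches the safety tables.

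**Working it through.** The plan states no figure to reproduce. The check is of logic and thresholds.

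**1. Can someone enter above the on-treatment limit?** Let *d* and *t* be the ULNs of direct and total bilirubin. Entry allows direct bilirubin up to 1.5*d*, and the Table 6 limit is 2*t*. A participant with total bilirubin at 2*t* passes entry if the direct share is at most 1.5*d* / 2*t*. The documents give no ULNs, so I assume *d* = 0.2 to 0.4 and *t* = 1.0 to 1.2 mg/dL:
- *d* = 0.2, *t* = 1.2: 0.30 / 2.4 = 12.5%
- *d* = 0.3, *t* = 1.2: 0.45 / 2.4 = 18.75%
- *d* = 0.4, *t* = 1.0: 0.60 / 2.0 = 30%

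Entry above 2 × ULN is therefore possible when roughly 70% to 87.5% or more of the bilirubin is unconjugated.

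**2. The row as logic.** Stop = (confirmed ALT > 2 × nadir) AND (bilirubin OR INR OR albumin item). If the bilirubin item is true at baseline and stays true, Stop = (confirmed ALT > 2 × nadir).

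**3. The ALT level that triggers it, in × ULN.**

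| ALT nadir | Row read alone | With ≥ 5 × ULN applied |
|---|---|---|
| 0.5 | > 1.0 | ≥ 5 |
| 1 | > 2 | ≥ 5 |
| 2 | > 4 | ≥ 5 |
| 4 | > 8 | > 8 |

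Read alone, a rise from 15 to 31 U/L qualifies (31/15 = 2.07).

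**4. The action it replaces.** Both milder rows require absence of hepatic toxicity, so they are closed to this participant. They are persistent ALT above twice baseline and ≥ 5 × ULN (continue treatment), and confirmed ALT ≥ 10 × ULN (hold, restart possible). Anyone who would otherwise fall there also meets the ALT half of the stopping row:
- ALT above twice baseline is above twice nadir, if nadir is no higher than baseline.
- Screening ALT must be below 5 × ULN (Cohort 2) or 2 × ULN (Cohort 1). If nadir is no higher than that, twice nadir is below 10 × ULN.

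Under either reading in step 3, the move is therefore from continue, or hold with possible restart, to permanent discontinuation. In Cohort 2 the hold row already starts TAF, so NUC treatment is an added consequence only below 10 × ULN.

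**5. One unchanged value, four yardsticks.** Take total bilirubin constant at 2.1 × ULN:
- Table 6 item: 2.1 > 2, met.
- Table 7 item: 2.1 / 2.1 = 1.0 × nadir, not above 2, so not met even before the Gilbert's exception.
- Monitoring end point of the same Table 6 row: already at baseline, so the bilirubin part is satisfied.
- Section 8.6.3: no grade increase, so not a treatment-emergent laboratory abnormality.

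**6. The confirmatory panel.** On treatment it lists total bilirubin only; in follow-up it lists total and direct. The fraction that governs entry is not in the panel behind the permanent stop, although routine chemistry collects it.

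**7. Size per participant.** 1/40 = 2.5 percentage points in Cohort 1 or Cohort 2 Group A. Group B (n = 20) no longer receives study treatment.

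**The case against.** A reader might infer that a constitutional bilirubin value forces discontinuation with no liver change at all. The documents do not support that. The row needs a confirmed ALT above twice nadir, and bilirubin alone triggers nothing. Nor does the point reach everyone with Gilbert's or raised total bilirubin: up to 2 × ULN the item is not met. The Table 6 actions are introduced as recommended, and Section 7.7 asks for the medical monitor to be consulted before discontinuation unless immediate action is warranted. These limits stand.

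The small-rise example depends on reading the row without the 5 × ULN condition. Since the row's ALT monitoring ends below 5 × ULN, a participant at 31 U/L would probably meet that exit at once, which favours applying the condition. That is a fair argument, but the neighbouring row states ≥ 5 × ULN and this one does not. Step 4 holds either way.

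Tables 6 and 7 serve different decisions, and participants who continue TAF in follow-up do not come under Table 7. An absolute on-treatment limit may be deliberate caution; it equals the Hy's law bilirubin limit in the same section. That is possible, and I do not say which definition is right. It does not explain why INR and albumin in the same row use baseline, or why an unchanged value counts as toxicity and as resolved.

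The consequence for the analysis is bounded. Participants who stop treatment stay in follow-up, and the FAS analyses them as assigned.

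**Conclusion.** The point holds as an inconsistency in a stopping rule. A total bilirubin above 2 × ULN is not barred at entry by any stated bilirubin limit, satisfies the Table 1/6 item from Day 1, and leaves the ALT condition to decide permanent discontinuation with bilirubin, INR and albumin unchanged. The hepatic-toxicity definition differs between Tables 1/6 and Tables 2/7, and the scope of the 5 × ULN condition is open.

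The size is small. It needs both an entry total bilirubin above 2 × ULN and a confirmed ALT more than double its nadir, and the documents give no frequency for either. Each case is 2.5 percentage points of a group of 40. That entry is possible is a matter of text; the direct shares in step 1 rest on assumed ULNs. Step 4 assumes that the ALT nadir is no higher than the screening and baseline values.

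**What to change.** - Reconcile the bilirubin definitions in Tables 1/6 and Tables 2/7 with each other, with the monitoring end point of the stopping row, and with what entry permits. If a difference is intended, say so. The clinical wording is for the sponsor's clinicians.
- State whether the 5 × ULN condition in the Section 7.7.5 lead-in governs the stopping row.
- In the clinical study report, flag hepatic-toxicity discontinuations in participants whose baseline total bilirubin already exceeded 2 × ULN.

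A change to exclusion 2(g) would achieve nothing, since enrollment is complete. The tables still apply to Cohort 1 and Cohort 2 Group A while dosing continues. The cost is wording in the body and synopsis tables and a letter to sites. The flag uses bilirubin data already collected.

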## 7.7.1. Grades 1 and 2 Laboratory Abnormality or Clinical Event

Continue study drug at the discretion of the investigator.

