## 7.7.2. Grade 3 Laboratory Abnormality or Clinical Event

- For Grade 3 laboratory abnormality or clinical event, study drug may be continued if the event is considered to be unrelated to study drug
- For any study drug-related, Grade 3 AE, study drug should be held
- For any study drug—related ≥ Grade 3 AE not able to be medically managed (eg, nausea with antiemetics), study drug should be permanently discontinued
- For a confirmed laboratory abnormality, study drug—related Grade 3, study drug would be held until toxicity returns to ≤ Grade 2. If a laboratory abnormality recurs to ≥ Grade 3 following rechallenge, study drug should be permanently discontinued, and the participant managed according to local practice. Recurrence of laboratory abnormalities considered unrelated to study drug may not require permanent discontinuation.

• For a Grade 3 clinical event, or clinically significant laboratory abnormality confirmed by repeat testing within 3 calendar days that is considered to be related to study drug, study drug should be withheld until the toxicity returns to ≤ Grade 2

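### Table 6 and synopsis Table 1 give no action for hepatic toxicity unless ALT has more than doubled from nadir, so a Hy's law pattern at stable, high ALT is left to discretion

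*Supplement*

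**What the plan says.** Section 7.7.5 governs on-treatment ALT rises through the three rows of Table 6, which synopsis Table 1 repeats. The actions are worded as recommendations.

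- **Row 1:** confirmed ALT ≥ 10 × ULN, no hepatic toxicity. Hold VIR-2218 and SLGN (and start TAF in Cohort 2), monitor weekly.
- **Row 2:** persistent ALT > 2 × baseline and ≥ 5 × ULN, no hepatic toxicity. Continue treatment; "ALT should be evaluated every 2 weeks or more frequently as clinically needed".
- **Row 3:** "Confirmed ALT > 2 × nadir, with evidence of hepatic toxicity, defined as any one of the following confirmed laboratory abnormalities". The abnormalities are bilirubin > 2 × ULN, an INR rise or an albumin fall. Permanently discontinue study treatment (TAF continues in Cohort 1; a NUC is started in Cohort 2), monitor weekly.

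The section's opening sentence also depends on a rise: ALT > 2 × nadir, or > 2 × baseline and ≥ 5 × ULN. The surrounding text adds "All elevated serum ALT should be confirmed as soon as possible and ideally within 3 days of receipt of results", with a clinical assessment and reflex tests. It defines Hy's law as ALT or AST > 3 × ULN with bilirubin > 2 × ULN, and its only provision for that pattern is "Liver biopsy may be collected for participants meeting Hy's law", where drug-induced injury is suspected.

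Outside the tables, section 7.7.1 says of Grade 1 and 2 findings "Continue study drug at the discretion of the investigator". For confirmed, drug-related Grade 3 laboratory findings, section 7.7.2 says "study drug would be held until toxicity returns to ≤ Grade 2". The laboratory hold in section 6.9.1 also starts at drug-related Grade 3 and leaves ALT out.

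**The concern.** Rows 1 and 2 exclude hepatic toxicity, and row 3 includes it only when ALT exceeds twice nadir. Hepatic toxicity with ALT at or below twice nadir has no row. No row uses AST, so the AST limb of the Hy's law definition has no row either in that situation.

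This matters where ALT starts high and stays high. Exclusion criterion 2d admits Cohort 2 participants with ALT up to just under 5 × ULN and Cohort 1 participants up to just under 2 × ULN. If bilirubin then rises past 2 × ULN while ALT barely moves, dosing can go on, with VIR-2218 to Week 20 and SLGN to Week 35. The hold and the retest interval are left to each investigator across about 30 centers.

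The ordering is also inverted. An ALT rise without hepatic toxicity is given a two-week retest interval, while the Hy's law pattern at stable ALT is given neither an interval nor a hold. Table 7, for follow-up with HBV DNA > LLOQ, acts on ALT > ULN with hepatic toxicity and asks for no doubling of ALT. Its bilirubin limit differs, but it shows that the plan does not treat doubling as necessary for action in that setting.

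**Working it through.** The plan states no figure to reproduce. The check is of the decision rules. ALT, AST and bilirubin are in multiples of ULN, and N is nadir ALT. The documents do not define nadir.

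**1. Example: nadir 4.0, ALT 4.5, bilirubin 2.2**
- Ratio to nadir: 4.5 / 4.0 = 1.125, not above 2. Row 3 does not apply.
- Hepatic toxicity is present (2.2 > 2), so rows 1 and 2 do not apply.
- Opening sentence: not met. ALT is not above 2 × nadir and is below 5. Baselines of 4.0, 4.5 and 4.9 all give this result.
- Hy's law limits: 4.5 > 3 and 2.2 > 2, so met.
- Grades (Appendix 11.5): ALT 4.5 lies in > 2.5 to 5, Grade 2; bilirubin 2.2 lies in > 1.5 to 2.5, Grade 2. Section 7.7.1 governs.

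The result is the same if hepatic toxicity is read as the laboratory criteria alone or as those criteria together with ALT > 2 × nadir.

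**2. Extent of the gap**
- Row 3 needs ALT > 2N and Hy's law needs ALT > 3. A gap exists when 2N > 3, that is N > 1.5.
- Drug-related ALT > 5 is Grade 3 and is held under 7.7.2; drug-related, clinically significant bilirubin > 2.5 is Grade 3 and is held under 6.9.1 and 7.7.2.
- The zone with no table action and no grade-based hold is therefore ALT above 3 up to min(2N, 5), with bilirubin above 2 up to 2.5.

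| Nadir N | 2N | ALT zone |
|---|---|---|
| 1.5 or less | 3 or less | none |
| 1.75 | 3.5 | 3 to 3.5 |
| 2.0 | 4 | 3 to 4 |
| 2.5 or more | 5 or more | 3 to 5 |

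In Cohort 1, screening ALT < 2 leaves a band of N about 1.5 to 2 and ALT about 3 to 4. If an ALT above 5 is not judged drug-related, the table gap runs on to 2N, which is 8.0 at nadir 4.0.

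**3. Doses still to be given**

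Section 6.5 places VIR-2218 at Day 1 and Weeks 4, 8, 12, 16 and 20, and SLGN weekly from Week 12 to Week 35 (24 doses).

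| Visit of abnormal draw | VIR-2218 left | SLGN left |
|---|---|---|
| Week 8 | 3 (Weeks 12, 16, 20) | 24 |
| Week 12 | 2 (Weeks 16, 20) | 23 (Weeks 13–35) |
| Week 20 | 0 | 15 (Weeks 21–35) |
| Week 32 | 0 | 3 (Weeks 33–35) |

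**4. Next scheduled safety test**

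Section 6.6 schedules safety laboratory tests at Weeks 4, 8, 12 and 14, then on to end of treatment. Assume 1 to 4 days for results (not given in the documents) plus the 3 days for confirmation, so confirmation falls on day 4 to 7.
- 28-day intervals: 28 − 7 = 21 to 28 − 4 = 24 days to the next test.
- 14-day intervals (Weeks 12–14 and 14–16): 14 − 7 = 7 to 14 − 4 = 10 days.

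Row 2 would give 14 days and row 3 would give 7. The ± 2-day visit windows can move these figures by a few days.

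**The case against.** The best counter-argument is that other provisions already reach this patient. Section 7.7.4 obliges the investigator to tell the medical monitor of any potential immune-related event, hepatic ones included, at any grade. Appendix 11.6 binds events considered nivolumab-related to the product label. This stands in part: for nivolumab-exposed participants in whom such an event is suspected, contact with the monitor is mandatory. But 7.7.4 sets neither a hold of SLGN or VIR-2218 nor a retest interval, and Appendix 11.6 applies only once the event is attributed to nivolumab. The remaining routes are unacceptable toxicity (6.9.1), extra visits (1.5) and following adverse events to resolution or stability (7.3.2). They rest on judgment or set no interval.

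Second, the Hy's law sentence adds suspected drug-induced injury, whereas the example has only the numeric limits in viremic hepatitis B with nearly unchanged ALT. That qualifier conditions the biopsy and does not supply a dosing rule. A relative-change trigger is reasonable for flares when high baseline ALT is allowed. It is less suitable once bilirubin has risen.

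Third, reach is small and time may be short. Entry excludes direct bilirubin > 1.5 × ULN, INR > ULN (unless on a stable anticoagulant), albumin < 3.5 g/dL and Cohort 2 candidates judged to need a NUC. Enrollment was complete at this amendment, Group B dosing has stopped, and some participants may be past treatment. All of this stands; it limits frequency and does not fill the gap.

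Fourth, the protocol's remark in section 5.4 that multiple-dose VIR-2218 safety is not well characterized introduces restrictions on hepatotoxic drugs, and section 1.4.4 reports good tolerability. That is fair, so the remark carries limited weight. Section 1.5 does, however, call the risk of the three-drug combination unknown.

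Finally, the example is not left without care: confirmation, clinical assessment, reflex tests and optional biopsy are described. What is missing is the hold and the interval.

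**Conclusion.** The gap is real and follows directly from the wording of the rows. Hepatic toxicity with ALT at or below twice nadir has no recommended action in Table 6 or synopsis Table 1. Within the zone derived above, no grade-based hold replaces it. It mainly concerns Cohort 2 Group A, with a narrow band in Cohort 1. The number of participants affected cannot be estimated from the documents and is probably small. The consequence per case depends on timing, from 3 VIR-2218 and 24 SLGN doses after a Week 8 draw to 3 SLGN doses after Week 32.

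The conclusion assumes nadir means the lowest ALT observed in the study. The 21 to 24 day figure also depends on the assumed 1 to 4 days for results. The existence of the gap does not. It is worth fixing because the rules, followed as written, give a potentially serious liver pattern less direction on retesting than an ALT rise without hepatic toxicity.

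**What to change.** Add one row to Table 6 and synopsis Table 1:

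- **Trigger:** confirmed ALT or AST > 3 × ULN with total bilirubin > 2 × ULN, in a participant without Gilbert's disease, whatever the ratio to nadir.
- **Action:** hold the remaining VIR-2218 and SLGN doses; monitor weekly until resolved; discuss with the medical monitor, including whether to start a NUC in Cohort 2.

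Add one sentence stating that this row applies regardless of the ALT thresholds in the section's opening sentence. Keep permanent discontinuation for ALT > 2 × nadir with hepatic toxicity. Isolated INR or albumin changes at stable ALT can stay under the general toxicity rules. The example would then trigger the new row (4.5 > 3 and 2.2 > 2).

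The cost is one row in two tables and one sentence in the next amendment, with the usual ethics and regulatory approvals. No new type of assessment is needed, and the weekly visits fall only on those affected. The downside is that a few participants with high, stable ALT may have doses held that they would otherwise have received.
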